8.4. Exclusion Criteria

1. Concurrent participation in another mechanical neurothrombectomy device trial or any other clinical trial with an active treatment arm or where the study procedure or treatment might confound the study analysis.

9. Study Procedures

9.1. Schedule of Events

Assessments and procedures for stroke management will be performed in this registry as per standard of care. Subjects enrolled into the registry will follow the schedule of assessments to be performed at each study visit as listed in the **Table 2**.

PR-NV-13514

Version A (13-MAR-2017)

Page 20 of 42

Table 2. Visit and Assessment Schedule

	Enrollment				Follow-up
Visit	Baseline	Procedure	24 hrs Post Procedure	≤ 7 days or Discharge	90-Day
Range			± 8 hrs		± 15 days
Day	0	0	1	7-10	90
Method	Clinic Visit	Clinic Visit	Clinic Visit	Clinic Visit	Clinic Visit or Phone
Demographics and Medical History	*				
mRS Assessment	•¹			•	•
NIHSS Assessment	♦ ²		♦ 4	•	♦ 6
ASPECTS	♦ ³				
Mechanical Thrombectomy		♦ 5			
Adverse Events		•	•	•	•
Discharge Disposition				•	

- 1. Pre-stroke mRS is completed at baseline by obtaining verification from an individual aware of the subject's functional status prior to stroke (e.g., family member, friend, etc.), as per standard of care. Pre-stroke mRS should reflect the subject's condition just prior to stroke onset. For example, if the subject was hospitalized during stroke onset, the subject's reason for hospitalization should be taken into account when evaluating the subject's pre-stroke mRS.
- 2. Pre-treatment NIHSS closest to start of procedure, as per standard of care.
- 3. ASPECTS evaluated from baseline imaging at enrolling hospital, as per standard of care.
- 4. Post-procedure NIHSS should reflect the latest score within the 24 ± 8 hour post procedure window, as per standard of care.
- 5. Required for subject to be eligible for the study.
- 6. Assessment will not be performed if visit is completed via phone

90-day Follow-up

The 90-day follow-up will be conducted as an office visit or via phone by the Investigator or research staff to collect information related to the subject's mRS and overall clinical condition. If the subject is unavailable for any reason, the subject's family/relative or caregiver/ legally authorized representative will be requested to provide the applicable information. A subject's participation in this prospective data collection registry will conclude at the completion of the 90-day follow-up. A follow-up electronic case report form (eCRF) will be completed for every subject that is enrolled into this registry, including subjects who prematurely discontinue.

PR-NV-13514

Version A (13-MAR-2017)

Page 21 of 42

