for Standardization (ISO)	fromvarious national standards organizations.	

[figure not shown]
PR-NV-13514

Version A (13-MAR-2017)

Page 7 of 42

Term	Definition	
Investigator	Individual member of the investigation site team designated and supervised by the principal investigator at an investigation site to perform critical clinical-investigation-related procedures or to make important clinical investigation-related decisions. (ISO 14155:2011 3.24). For the purposes of the protocol, 'Investigator' also refers to the Principal Investigator.	
Modified Rankin Scale (mRS)	Commonly used scale for measuring the degree of disability or dependence in the daily activities of people who have suffered a stroke or other cause of neurological disability. It has become widely used in clinical outcome measures for stroke clinical trials. Scale for measuring general neurologic function: 0 No symptoms at all	
	 No significant disability despite symptoms; able to carry out all usual duties and activities Slight disability; unable to carry out all previous activities, but able to look after own affairs without assistance Moderate disability; requiring some help, but able to walk without assistance Moderately severe disability; unable to walk without assistance and unable to attend to own bodily needs without assistance Severe disability; bedridden, incontinent and requiring constant nursing care and attention 	
National Institutes of Health Stroke Scale (NIHSS)	6 Dead Method for quantifying neurological deficits developed by the National Institutes of Health. It is used to assess the severity of a stroke.	
Neurological Death	Death due to neurological cause	
Principal Investigator	Qualified person responsible for conducting the clinical investigation at an investigation site. (ISO 14155:2011 3.33).	
Screen Fail	Subject who sign the Informed Consent form and is identified later as failing to meet all inclusion/exclusion criteria.	
Sponsor	A person who initiates a clinical investigation, but who does not actually conduct the Investigation, i.e., the test article is administered or	

Page 8 of 42

Term	Definition		
	dispensed to or used involving, a subject under the immediate direction		
	of another individual.		
Symptomatic intracranial	≥ 4 points worsening from baseline on the NIHSS scale associated with		
hemorrhage (sICH)	an image finding of intra-cranial hemorrhage (i.e., intracerebral or		
	intraventricular) at 24 +/- 8 hrs post procedure.		

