5.1.1.1. Primary Endpoint

The following will be assessed:

Modified Rankin Scale (mRS) at 90 days.

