5.1.2.2. Additional Evaluations

The following additional assessments for evaluation will be completed:

- Revascularization at the end of the procedure using mTICI score (0, 1, 2a, 2b, 3)
- Workflow metrics (e.g., time from onset to door, time from door to imaging, time from imaging to puncture, time from door to revascularization, etc.)
- Post-acute discharge disposition: discharge to home or any other type of facility (e.g. rehabilitation services, nursing facilities, hospice, etc.)
- National Institutes of Health Stroke Scale (NIHSS) score at hospital discharge or ≤ 7 days post index stroke procedure, whichever comes first.
- Subject disposition at study exit

6. Study Design

This is a prospective, multi-center, non-randomized, observational registry of AIS patients that have or will undergo treatment with the use of a Medtronic market-released neurothrombectomy device (as the initial device used to remove the thrombus) within 8 hours of stroke symptom onset. This registry aims to collect real world data on patients in whom the decision of device use has been made prior to data collection. This registry does not aim to affect patient care, but rather only to document outcomes observed during standard of care stroke management practice at investigation sites.

Methods incorporate to minimize bias were considered and up to 500 subjects will be enrolled at up to 15 sites in Singapore, Thailand and Vietnam. Each site is expected to enroll a minimum of 10 subjects, not to exceed a maximum of 75 subjects per site to ensure wide spread distribution of data. Sponsor approval must be obtained prior enrolling additional subjects.

All study clinicians and Medtronic/study personnel will be trained on the corresponding aspects of the study using standardized training materials and required to follow the CIP. Subjects may be enrolled in this registry from the point of arrival at the enrolling hospital where treatment with a Medtronic market-released neurothrombectomy device is to occur, up to the day of hospital discharge, or \leq 7 days after index stroke procedure, whichever comes first. The baseline through discharge visits will take place

PR-NV-13514 Version A (13-MAR-2017)

Page 16 of 42

Medtronic

at the treating hospital. Subject's participation in this prospective data collection registry will conclude at the completion of the 90-day follow-up.

An overview of the registry flow is depicted in Figure 1.

[figure not shown]

Figure 1. Registry Flowchart

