13.2. General Principles

The primary analysis for all baseline characteristics and study outcomes will include all enrolled subjects treated with Medtronic market-released neurothrombectomy devices. All available data will be included in primary study analyses. Standard summary statistics will be calculated for all study variables. For continuous variables, statistics will include means, standard deviations, medians and ranges. Categorical variables will be summarized in frequency distributions. One-sided statistical tests will have p-values less than 0.025 deemed significant while two-sided tests will have p-values less than 0.05 deemed significant. All testing will be performed using a two-sided test at a 0.05 level of significance or a one-sided test at a 0.025 level of significance.

All statistical analyses will be performed using SAS (version 9.2 or higher, SAS Institute Inc. Cary, NC), R (version 3.0 or higher, R Foundation for Statistical Computing, Vienna, Austria) or other widely accepted and validated statistical or graphical software.

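### The 90-day mRS, the sole primary endpoint, may be rated by anyone on the site team, including the operator, in clinic, by phone or through a proxy, with no common structured interview and no planned summary by mode, informant or rater

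*Combined protocol and SAP*

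**What the plan says.** Section 5.1.1.1 names one primary endpoint, "Modified Rankin Scale (mRS) at 90 days", and Section 13.4 repeats it. Neither section defines a cut-point or an ordinal summary.

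Section 9.1 sets out how it is collected: "The 90-day follow-up will be conducted as an office visit or via phone by the Investigator or research staff". The informant can change too. "If the subject is unavailable for any reason", the "family/relative or caregiver/ legally authorized representative will be requested to provide the applicable information".

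The Glossary defines an Investigator as a member of the site team designated "to perform critical clinical-investigation-related procedures or to make important clinical investigation-related decisions", and the term also covers the Principal Investigator. Treating physicians are not excluded.

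Mode of contact matters elsewhere in the same schedule. For the 90-day NIHSS, note 6 to Table 2 says "Assessment will not be performed if visit is completed via phone". The mRS is kept at phone visits without any added condition.

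On analysis, Section 13.2 says "All available data will be included in primary study analyses". Section 13.4 plans descriptive summaries and allows comparison or pooling with similar sponsor studies. Section 13.5 names subgroups by NIHSS and by discharge disposition and says they will be compared statistically. Section 13.6 scores deaths as mRS 6. Mode, informant and rater appear nowhere in Section 13.

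**The concern.** The mRS is a judgement, and the Glossary shows where it is hardest. Level 2 means looking after one's own affairs unaided, and level 3 means needing some help. Who asks, how they ask and who answers can move a subject across that line. A rater who performed the procedure knows how it went and has an interest in the result. A relative may describe the same subject differently from the subject, and a phone call gives no direct observation.

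With a single cohort, no control arm absorbs such a shift, so it falls directly on the reported distribution. It can also reach three further results:

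- Comparisons by discharge disposition, because subjects discharged to a facility may more often be rated through a proxy.
- Any pooling or comparison with other sponsor studies, since Section 13.4 does not ask for the same rating method.
- Any informal reading against the 46% functional independence cited in Section 6.2.

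A larger sample narrows the interval but does not remove the shift, and the planned tables would not show it.

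**Working it through.** **Controls in the plan.** Each provision that might cover rating was checked.

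- Section 6 and Section 15.4: general study training with standardized materials. No mRS certification or interview is named.
- Section 12: the Steering Committee's listed roles do not include adjudication or central reading of the mRS.
- Section 15.5: monitoring addresses data accuracy and compliance. Checking against source does not test whether a rating was generous.
- Section 13: no adjustment, stratification or sensitivity summary by mode, informant or rater.

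**Plan figures.** The sample size of 500 rests on no power or precision formula (Section 13.5), so there is nothing to reproduce for it. The one checkable figure there agrees: 75 ÷ 500 = 15%.

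**Sampling error for scale.** Inputs: p = 0.46 (Section 6.2) and n = 500 (Section 13.5).

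- Half-width = 1.96 × √(p(1 − p)/n) = 1.96 × √(0.46 × 0.54/500) = 0.0437, or 4.4 points.
- With 400 rated subjects it would be 4.9 points.

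**Illustrative rating shift.** Let s be the share of subjects truly at mRS 3 and u the share of those rated 2 instead. The assumed ranges are s = 10-20% and u = 10-30%. Neither is in the documents. Shift in mRS 0-2 = s × u.

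| s | u | Shift (points) |
|---|---|---|
| 0.10 | 0.10 | 1.0 |
| 0.10 | 0.30 | 3.0 |
| 0.15 | 0.20 | 3.0 |
| 0.20 | 0.30 | 6.0 |

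In the full frequency distribution, the same number of points leaves level 3 and joins level 2.

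**How often the shift exceeds the half-width.** At s = 0.20 it needs u above 0.0437 ÷ 0.20 = 0.22. At u = 0.30 it needs s above 0.0437 ÷ 0.30 = 0.146. Treating both ranges as uniform, the share of the grid above 0.0437 is

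[0.30 × (0.20 − 0.1457) − 0.0437 × ln(0.20/0.1457)] ÷ (0.10 × 0.20) ≈ 0.12.

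So the shift exceeds the sampling half-width in about 12% of the assumed grid.

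**What a smaller shift would do.** The plan does not specify a test against 46%. If someone made one (two-sided, 0.05) when the true rate was 46%, a shift of b points would give a false difference with probability of about Φ((b − 1.96·se₀)/se₁), plus a negligible opposite tail. Here se₀ = √(0.46 × 0.54/500) = 0.0223 and se₁ is the same expression at 0.46 + b. For b = 0.03, se₁ = 0.0224 and (0.03 − 0.0437)/0.0224 = −0.61, giving 27%. For b = 0.01 and 0.02 the results are 7% and 15%, against a nominal 5%.

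**The case against.** The strongest reply is that this is an observational registry documenting standard care. Outcomes are summarized descriptively, and no hypothesis stands behind the sample size. Operator-independent rating belongs to trials. The size of the problem is wholly assumed, counts only errors from 3 to 2, and uses an mRS 0-2 cut that the plan never makes its endpoint. Training materials, a study training plan, eCRF Completion Guidelines and a Clinical Monitoring Plan exist and may already cover rating. A table by mode or informant would be confounded, because proxies and phone calls may be used more for sicker subjects.

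Much of this stands. The magnitude is illustrative, errors from 2 to 3 would push the other way, and the direction of proxy and phone effects is not given. mRS 0-2 appears only as background in Sections 4.1 and 6.2. The table cannot isolate rating bias. The open wording of the subgroup list in 13.5 does not forbid a tabulation by mode, and the all-available-data rule in 13.2 concerns inclusion, not how ratings are made.

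It does not close the gap. A descriptive study still reports an mRS distribution as its main result, Section 13.5 plans statistical comparisons among subgroups, and Section 13.4 allows external comparison. A common question set changes no care.

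A reader might go further and infer that the endpoint is unmasked in the trial sense, that operators will do the rating, or that mode and informant are not recorded. The documents support none of these. Section 6 describes "This is a prospective, multi-center, non-randomized, observational registry of AIS patients", so there is no allocation to mask. Rating by the operator is permitted, not shown to occur. The documents do not say what the 90-day eCRF captures, and the phone rule for the NIHSS suggests that mode is known.

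**Conclusion.** The point holds as a gap in how the sole primary endpoint is measured and reported. Rater, mode and informant differences can enter the mRS distribution among survivors, and nothing planned would show them. Deaths are immune.

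Direction and size are unknown from the documents. Under the stated one-directional assumptions the mRS 0-2 proportion rises by 1.0 to 6.0 points, 3.0 at the midpoint, against a 4.4-point half-width. It would be wrong to conclude that rating bias is likely to exceed sampling error, since that needs the upper corner of both assumed ranges. A shift below the half-width still matters, because it adds to sampling error and does not shrink with n. This is a low-cost improvement worth making, not a flaw that invalidates the registry.

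**What to change.** - **Section 9.1.** State that the 90-day mRS is rated by a trained Investigator or research staff member who did not take part in the index procedure, using one fixed structured mRS question set for clinic, phone and proxy contacts. Where a site has no such person available, the rating still goes ahead and the rater's role is recorded. Investigators who were not involved in the procedure remain eligible, and phone and proxy contacts stay allowed, which protects follow-up.
- **90-day eCRF.** Record mode, informant and rater role, if not already captured.
- **Section 13.4.** Show the 90-day mRS distribution overall and by mode, informant and rater role as a descriptive sensitivity summary. Note beside it that phone and proxy use may be confounded with severity, so differences are not estimates of rating bias.

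The cost is a short change to 9.1, up to three eCRF fields and one table. A site would not normally use the operator as rater. Raters may still know the clinical course, so the bias is reduced, not removed. No new staff or visits are required, and treatment and sample size do not change.

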9.2. Subject Screening

Given that the prospective study population consists of patients who have or will undergo treatment with the use of a Medtronic market-released neurothrombectomy device and that the screening assessments consist of standard patient diagnostics for this therapy, subjects are considered enrolled in the study once the subject has signed and dated the informed consent. If the subject signs the Informed Consent form and is identified later as failing to meet all eligibility criteria, the subject will be classified as a screen failure. Upon determination that the subject does not qualify for enrollment, the reason for the subject's screen failure status will be documented on a Screening and Enrollment Log, in order to minimize bias. No eCRFs in the Electronic Data Capture (EDC) system are required to be completed for screen failure subjects.

9.3. Medical History

Relevant stroke related medical conditions listed in the eCRFs that present prior to the Medtronic market -released neurothrombectomy device procedure (i.e., from subject's arrival at the enrolling hospital through the index procedure), should be documented under medical history.

9.4. Subject Consent

The Principal Investigator or his/her authorized designee will conduct the informed consent process and ensure the nature and objective of this registry is thoroughly explained to the subject and/or subject's legally authorized representative (LAR) in the language understood by the subject/subject's LAR. The subject must have ample time and opportunity to read and understand the ICF, to inquire about details of the study, and to decide whether or not to participate in the clinical study. All questions about the study should be answered to the satisfaction of the subject. Language used should be non-technical and should not waive or appear to waive the subject's legal rights. The consent process can occur at any point during the enrollment period (from the point of arrival at the enrolling hospital where treatment for their index stroke with a Medtronic market-released neurothrombectomy device has occurred, up to the day of hospital discharge or ≤ 7 days post index stroke procedure, whichever comes first). The consent process will be done according to country regulations and/or IEC.

The Principal Investigator is responsible for ensuring informed consent form (ICF) is obtained from each subject and/or subject's LAR prior to subject enrollment and entering of any subject data into the registry database. Informed consent must be documented prior to any procedure specific to the clinical study is applied to the subject.

The ICF is required and must be obtained in a format approved by the IEC. The form should contain standard language consistent with local policies for ensuring privacy of confidential information. The ICF must be reviewed and approved by the Sponsor prior to submission to the appropriate IEC for approval.

PR-NV-13514

Version A (13-MAR-2017)

Page 22 of 42

The Investigator is responsible for ensuring any new information related to the registry will be provided to the subject and/or subject's LAR, if applicable. Subject may need to be re-consented to continue participation in the registry, as required by country regulations and/or IEC.

After all persons have signed and dated the informed consent form, the investigator must provide the subject with a copy of the signed and dated informed consent form.

9.5. Assessment of Safety

Assessment of safety shall be based on the following:

- Incidence of symptomatic Intracranial hemorrhage (sICH) at 24 hrs ± 8 hrs post procedure
 - o sICH: \geq 4 points worsening from baseline on the NIHSS scale associated with an image finding of intra-cranial hemorrhage (i.e. intracerebral or intraventricular) at 24 ± 8 hrs post procedure.
- All-cause mortality through 90 days post procedure
- Incidence of emboli in new territory (ENT) at 24 hrs ± 8 hrs post procedure
 - o ENT: Embolization territories outside of the target downstream territory

9.6. Recording Data

Study data will be collected using eCRFs and stored in a validated, password protected electronic data capture (EDC) system. The system allows the capability of data collection remotely through the internet so the participating investigation site personnel may log on to the system securely and enter the data. All subjects' data collected in the system will be extensively verified through data validation programs, database integrity rules, and investigation-specific data entry conventions for data accuracy and logical meaningfulness. Data entered on eCRFs will be derived from source documents, which may include worksheets and patient medical records. Periodic review of all subjects' collected data will be performed in order to examine the expected distributions of data and to identify outliers for possible data entry errors.

The Principal Investigator is responsible for reviewing all eCRF entries for completion and correctness. Changes in case report forms will be made electronically and the system used will keep an audit trail of changes. If necessary, an explanation for the change(s) may be provided. The Principal Investigator will electronically approve all eCRF data.

All study staff that enter data into eCRFs will undergo appropriate training for use of eCRFs. Further information regarding eCRF navigation and use may be found in the eCRF Completion Guidelines.

PR-NV-13514

Version A (13-MAR-2017)

Page 23 of 42

9.7. Deviation Handling

This registry is designed for the collection of real-world data for acute ischemic stroke patients treated with Medtronic market-released neurothrombectomy devices in the clinical setting. The clinical investigational plan (CIP) does not mandate specific care or visits not considered standard of care at the treating hospital and therefore would not be considered a protocol deviation if not completed.

A CIP deviation must be reported for the following situation:

- Failure to properly obtain informed consent per GCP, IEC and/or local institutional policies
- Failure to report SAEs within the reporting timelines as described in Section 11.2
- Failure to complete protocol training prior to performing study related activities

All deviations shall be entered as soon as possible in the electronic data capture system. Protocol deviations will be routinely reviewed by the Sponsor's study team. Where deviations occur, investigation sites are expected to implement corrective actions to prevent reoccurrence. Investigation sites with a high rate of protocol deviations will be closely monitored. If an investigation site demonstrates lack of compliance with the protocol and continuous protocol deviations are noted, the clinical site may be suspended from enrolling additional subjects or terminated from the study at the Sponsor's discretion.

